## **5.0 Procedures Involved**

**Study Design:**

This is a randomized, double-blind, placebo-controlled clinical trial in 40 adults at least 18 years of age with SCI. Participants who meet the eligibility criteria (described in Section 8.1) will be randomly assigned with a 1:1 ratio to active drug (escalating brivaracetam dose to 100 mg twice daily for four weeks) or placebo using a randomization schedule developed by our biostatistician. This is a simple computer generated 1:1 scheme that randomly assigns participants to arm C or arm D. Study participants, research coordinators, and study personnel involved in outcomes assessments and analyses will all be masked to allocation. The drug will be provided by RxArtisans pharmacy in Wayzata, MN. The active and placebo capsules will have identical appearance and consistency. Treatment assignment will be known only to the investigational drug pharmacy (RxArtisans). We will register this trial at [www.clinicaltrials.gov](http://www.clinicaltrials.gov).

Study Procedures:

Overview of study procedures/study interventions. This study involves research activities that occur in-person, over the phone, and via online REDCap surveys. Participants will also have the option to participate entirely remotely. In this circumstance, there will be no MRI scan nor blood draw for banking; instead, all required safety labs will be completed with the participant's primary care physician and insurance will be charged and the participant will be responsible for any associated copays or costs. All research activities are summarized in Table 1 below and described in detail in the subsequent text.

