Screening: A phone screen will be administered to confirm basic eligibility criteria listed in Section 8.1 such as age, pain level, medication use, and other medical conditions. Study staff will also screen for MRI contraindications at that time with the Center for Magnetic Resonance Research (CMRR) pre-screening questionnaire (i.e., implanted medical devices or retained metal fragments). Eligible individuals will be required to receive medical clearance from their primary care provider within one month of (prior to) Visit 1, including physical exam, health history, and lab work to confirm normal renal function, absence of liver cirrhosis, and absence of pregnancy. While we will target obtaining lab work within 1 month of baseline, labs up to 6-weeks prior to baseline will be accepted to reduce participant burden. Their insurance will be charged, and they will be responsible for any associated copays or costs.

For participants who recently had comprehensive metabolic panel done, medical record review of lab results can replace new screening labs if the blood labs were completed within one month of (prior to) the scheduled baseline appointment. If the participant is seeing a provider in-system, the study coordinator will pull labs from the medical record. If the participant is not seeing a provider in-system, the study coordinator will instruct the participant's physician to fax the lab report to the study coordinator. The instructions for faxing will be on the screening eligibility sheet the participant brings to their doctor's appointment and available to be emailed for the participant upon request.

Visit 1: This visit includes informed consent, randomization, a focused physical exam, and a mental health and health history screen. CDE-recommended questionnaires relating to pain, mood, active suicidality, satisfaction with life, kinesiophobia, sleep quality, and community integration will also be administered.

Visit 2: This visit may be combined with Visit 1, if the participant prefers. Visit 2 includes an optional blood draw for batch analysis and an optional MRI scan; the optional MRI and optional blood draw are paid for by the study. Visits 1 and 2 can take place either at the study site or virtually, depending on participant preference. Those who choose to participate in the study virtually will not take part in the MRI or blood draw. For participants with contraindications to MRI, the MRI will not be completed.

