Once randomized, the 7-week supply of study drug will be dispensed and mailed directly to participants to begin 7 weeks of active treatment or placebo, as described in Section 4.0. All participants will receive a medication diary to track study drug compliance and to record medication use.

Weekly phone check-in: Masked data collectors will perform weekly check-in calls to assess for medication-related adverse events (AEs). The data collector will also administer the Patient Health Questionnaire 9-item (PHQ-9) to assess for changes in mood and suicidality. A suicide protocol will be initiated if a participant endorses suicidality (see below). Participants will also report on their level of pain (rate highest, lowest, and average pain (0-10) that day). Reported AEs identified in these calls will be documented and immediately shared with the PI for review.

Suicide Protocol: Endorsement of active suicidality on PHQ-9 will trigger the suicide protocol. Study staff will call 911 in the event of a psychological emergency noted during a phone call (credible report of intent to harm oneself). Study staff will first ask to speak to another adult in the household. If none is present or comes to call, study staff will call 911 and remain on the line until first responders arrive. In the event of a non-emergent psychological situation (psychological distress in the absence of intent for self-harm), study staff will refer the participant to their PCP or the National Suicide Hotline ([name]). In either case, study staff will notify the PI immediately.

Visit 3: End of intervention assessments will be repeated 5 weeks after Visit 2. This includes a focused physical exam, a mental health and health history screen, optional blood draw, optional MRI, and questionnaires relating to pain, mood, active suicidality, satisfaction with life, kinesiophobia, sleep quality, and community integration. Additionally, limited safety labs will be repeated (from pre-Visit 1) to confirm normal renal function, absence of liver cirrhosis, and absence of pregnancy in individuals of childbearing potential. The fasting blood draw and analysis

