
*Intervention Expectations.* This self-report will assess what participants expect their outcomes to be during and after their participation in the study.

*Study Expectancies.* Participants respond to 24 items about how they think they will function 7 weeks from now in areas such as pain, sleep, participation, work, social activities, and sexual functioning.

*Concurrent Pain Medication Use.* Although pain medications can confound the analgesic effects of brivaracetam, we consider it to be unethical to require participants to discontinue pharmacologic treatment for pain over the course of the study as a criterion for enrollment. In addition, to increase generalizability, it is important to recruit participants using pain medications. Therefore, we will record pain medication use over the course of the trial and consider this in the analysis.

*Pain Intensity and Medication Use Diary.* We will monitor daily pain reports and patient medication throughout the course of the study using a Pain Intensity and Medication Use Diary. Participants will be asked to record daily pain ratings (highest pain 0-10, lowest pain 0-10, and average pain 0-10) and any pain medication use. This diary will be started 1 week prior to drug treatment and maintained until completion of the study.

*Assessment of Brain Function with MRI.* All scans will be performed on the same scanner for this study. We will use the Siemens 3-T Prisma multi-band scanner. Prior to each scan, participants will be asked five questions regarding their pain now and over the last week as well as alcohol, caffeine, and tobacco use over the past 12 hours.

1. Structural MRI acquisition: We will acquire a T1-weighted Magnetization-Prepared Rapid Acquisition with Gradient Echo (MPRAGE) image [Repetition Time (TR)=2.5s, Echo Time (TE)=4.5ms, 0.8mm^3 voxels], and a T2 weighted Sampling Perfection with Application optimized Contrasts using different flip angle Evolution (SPACE) image [TR=3.2s, TE=565ms, 0.8mm^3 voxels]. We use special sequences for the scans to reduce the impact of head motion.

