**Table 1. Study Procedures**

Study Task	Screening	Visit 1 b	Visit 2 b	7-week intervention	Visit 3 c (end of study testing)	Visit 4 c
Screening Phone Survey	X					
Consent/randomization		X				
MRI Brain Scan (optional)			X		X	
Blood draw for biomarkers (optional)			X		X	
Physical health exam, health history screening		X			X	
Surveys		X			X	X c
Dispense study drug			X			
7-week drug intervention				X		
Limited safety labs (blood draw, required)	X a				X	
Pregnancy test (for women of child-bearing potential)					X	
Drug dose reduction protocol					X c	
Participant return remaining pills, bottle, and medication diary via mail					X c	
Adverse Events, PHQ-9, pain rating (highest, lowest, average)				Assessed weekly c		

PHQ-9: Patient Health Questionnaire 9-item

aMedical clearance must be clinically obtained from participants' primary care provider or other healthcare provider within 1 month prior to visit 1

bVisits 1 and 2 may be combined for participant convenience

cPerformed at the time of early withdrawal for those not completing the study

**Study drop criteria:** Participants will be removed from the study for safety reasons including drug intolerance, drug allergy, drug contraindications, development of depression, aggressive behavior, anxiety, or suicidality, or evidence of brivaracetam adverse events according to the manufacturer's prescribing guide (package insert). Poor drug compliance will be recorded for consideration during the analysis but will not be cause for removal from this study. In the case of drug intolerance, participants will reduce the drug dose under medical supervision of the PI until the drug can be safely discontinued.

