#### Screening:

A phone screen will be administered to confirm basic eligibility criteria listed in Section 8.1 such as age, pain level, medication use, and other medical conditions. For those that agree to have an MRI, we will screen participants for contra-indications for MRI compatibility with the CMRR pre-screening questionnaire. If participant meets basic eligibility requirements, we will request that they obtain medical clearance for study participation from their primary care provider or other medical professional, including collecting 3-4 tablespoons of blood for screening blood work (described in detail below) and completing a physical exam and health history. This must be conducted within 1 month (or up to 6-weeks) of Visit 1. The participant's insurance will be charged, and they will be responsible for any associated copays or costs.

The participant's provider will send research staff the results via fax or email, or the participant may carry a hard copy to Visit 1. If a patient is part of the enrolling site's system of care, their medical records will be accessed directly by research staff who have obtained the appropriate approvals (e.g., NERS approval).

*Screening bloodwork for hepatic cirrhosis, renal insufficiency, and pregnancy.* Brivaracetam treatment is not safe for those who are pregnant, have hepatic cirrhosis, or kidney dysfunction. Therefore, to be medically cleared to enter the study, participants must complete a fasting blood draw through their primary care clinic for analysis of blood urea nitrogen (BUN), creatinine, alanine transaminase (ALT), aspartate transaminase (AST), total bilirubin, albumin, GFR, calcium, corrected calcium, and human chorionic gonadotropin (hCG); urine hCG test will also be accepted. International normalized ratio (INR) will be collected at the discretion of the participant's primary care provider if the participant is on anticoagulation or has abnormal liver function tests. People who are menopausal and have not had a menstrual period for at least 12 months, or people who have had a hysterectomy will not be required to take pregnancy tests. We will use lab work performed clinically during any recent visit (within one month or up to 6-weeks of testing) for screening labs when available. Any participant found to have renal insufficiency (GFR<60ml/minute), hepatic cirrhosis, Child-Pugh grades A, B, and C, or pregnant (positive hCG) will be considered a screen fail and will not progress in the study.

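### Randomisation is fixed at Visit 1, before the diary week and, when visits are separate, before the optional baseline MRI and blood draw; it should be the last step before drug is released

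*Combined protocol and SAP*

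**What the plan says.** Section 5.0 (Study Procedures, Visit 1) lists the content of the first visit: "This visit includes informed consent, randomization, a focused physical exam, and a mental health and health history screen". Table 1 has one row, "Consent/randomization", marked in the Visit 1 column. Neither place gives an order within the visit.

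Eligibility is addressed elsewhere. Section 5.0 (Study Design) states: "Participants who meet the eligibility criteria (described in Section 8.1) will be randomly assigned with a 1:1 ratio". The screening text adds: "Eligible individuals will be required to receive medical clearance from their primary care provider within one month of (prior to) Visit 1". Section 8.0 (Screening) says that anyone failing on renal function, cirrhosis or pregnancy "will be considered a screen fail and will not progress in the study". The same section lets the participant bring the clearance results to Visit 1 on paper.

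On baseline data, Section 5.0 says: "Visit 2 includes an optional blood draw for batch analysis and an optional MRI scan". Visits 1 and 2 may be combined if the participant prefers. Section 11.0 (Payment) describes Visit 2 as the baseline testing visit. Of the pain diary, Section 5.0 says: "This diary will be started 1 week prior to drug treatment and maintained until completion of the study".

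On drug release, the text after Visit 2 reads: "Once randomized, the 7-week supply of study drug will be dispensed and mailed directly to participants". Table 1 marks dispensing under Visit 2.

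**The concern.** In a trial analysed by intention-to-treat (Section 15.1), everyone randomised counts. Assignment is therefore best made when nothing remains to be done except start the drug. Here it is made at the consent visit. Any withdrawal, late-noticed exclusion or failed baseline procedure between that visit and the first dose then belongs to a randomised participant. Section 15.1 gives no rule for such people. They either contribute outcomes with no exposure to drug, which dilutes the effect, or they contribute no outcome.

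There is a second, smaller stake. Aim 3 uses baseline miR-485 and Aim 2 uses pre-post imaging change. If drug could reach a participant before the Visit 2 scan and blood draw, those measurements would no longer be baseline.

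**Working it through.** The plan states no figure on this point, so the check is to put the steps in order, count the weeks, and then give an illustration of size.

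**1. Eligibility.** The phone screen names age, pain level, medication use and other medical conditions as examples. Primary-care clearance covers physical exam, history and labs. Both precede Visit 1. Past or current suicidality and active psychiatric treatment are exclusions in Section 8.0, and the first step that names mental health or suicidality is Visit 1. Paper clearance results may also first reach staff there. These items share a visit with randomisation, with no stated order. The rest of the eligibility work is already done.

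**2. Baseline.** Section 6.1 says all data are obtained after consent, and consent is at Visit 1. A seven-day diary therefore cannot be finished before a Visit 1 randomisation, whether or not the visits are combined. The optional MRI and blood draw follow randomisation whenever Visit 2 is a separate visit. The pain questionnaires are at Visit 1.

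**3. Drug release.** The Section 5.0 text makes randomisation the trigger. Table 1 places dispensing at Visit 2. With separate visits, a literal reading of the text allows drug to leave before the Visit 2 scan and blood draw; Table 1 does not.

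**4. Weeks.**
- Section 4.0: dosing before Visit 3 is 1 week + 28 days = 5 weeks.
- Section 5.0: Visit 3 is 5 weeks after Visit 2.
- Diary week plus dosing: 1 + 1 + 4 = 6 weeks.

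With separate visits the diary week fits between Visits 1 and 2, which is after randomisation. With a combined visit, the diary starts that day at the earliest and the first dose falls at week 1, so five weeks of dosing end at week 6. Visit 3 is set at week 5, and the schedule is one week short.

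**5. Size (illustration).** Inputs: the 2-point effect from Section 15.2 and up to 48 enrolled from Section 10.0. The number *k* randomised but never dosed is an assumption; the documents give none. Assume also that the *k* are split evenly between arms, show no drug effect, and still have outcomes measured.

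Diluted effect = 2.0 × (1 − *k*/48)
- *k* = 2: 2.0 × 46/48 = 1.92
- *k* = 4: 2.0 × 44/48 = 1.83

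With the 40 participants named under Study Design as denominator, the values are 2.0 × 38/40 = 1.90 and 2.0 × 36/40 = 1.80.

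To express this as power, an SD of change is needed, which the plan does not give. Take the value at which 20 per arm has exactly 80% power for 2 points (normal approximation, two-sided 5%):

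SD = 2 / [(1.960 + 0.842) × √(2/20)] = 2.26

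At that SD and 20 per arm, power is about 77% for *k* = 2 and 73% for *k* = 4. If the outcomes are missing instead, the losses are 2/48 = 4.2% and 4/48 = 8.3% of those randomised.

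**The case against.** The strongest reply is that the protocol already has an eligibility gate. A reader might infer from Visit 1 that people are randomised first and checked for eligibility afterwards. The documents do not support that. Study Design conditions assignment on meeting the criteria, the main exam, history and labs come earlier, and laboratory screen failures go no further. The exam and the mental health screen at Visit 1 recur at Visit 3, so they also serve as paired assessments. Nor does any section say that suicidality or psychiatric treatment goes unchecked until Visit 1. This part of the reply stands, and it confines the eligibility gap to unstated order within one visit.

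A reader might also infer that drug is sent before the baseline scan and blood draw. Table 1 dispenses at Visit 2, and Visit 3 is timed from Visit 2 by an interval equal to the planned dosing, so treatment appears to be counted from Visit 2. The mailing sentence can be read as a precondition. This is a conflict of wording to be reconciled, not a demonstrated post-dose baseline, and it touches only optional procedures in exploratory aims.

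Finally, the primary endpoint is little exposed. Its questionnaires are at Visit 1, the diary is pre-drug by definition, and masking of participants and assessors limits bias in baselines taken after assignment but before dosing. Table 1 also provides for assessments at early withdrawal, so a loss need not leave a blank. That helps only in part, because an assessment at withdrawal before dosing is not the five-week outcome.

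None of this supplies the missing order, lets the diary week finish before a Visit 1 randomisation, or resolves the text against Table 1.

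**Conclusion.** The point holds in a limited form. Followed as written, the plan randomises every participant before the diary week is complete and, when visits are separate, before any optional MRI and blood draw. The eligibility gap is narrow. The text and Table 1 disagree on what triggers drug release and must be reconciled.

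The consequence is mainly efficiency: avoidable pre-dose losses inside the intention-to-treat set. Its size is unknown. Two to four such participants among 48 would reduce a 2.0-point effect to 1.92 to 1.83, but those counts are assumed, and the power figures rest on a further assumption about the SD. A possible post-dose measurement labelled as baseline in Aims 2 and 3 depends on the literal reading of the mailing sentence. The documents do not support a claim that the randomised comparison of pain is biased. This is an inexpensive improvement worth making.

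**What to change.** Make assignment the last step before drug is released. State in Section 5.0 that study staff request assignment from the pharmacy only when all eligibility items, including those seen at Visit 1, have been reviewed, and when the Visit 1 questionnaires, any chosen Visit 2 MRI or blood draw, and the diary week are complete. Drug is released after that.

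The edits that follow:
- Table 1: take randomisation out of the Visit 1 consent row and give it its own row and position, before dispensing.
- Section 5.0: align the Visit 1, Visit 2, drug-mailing and diary paragraphs with that order.
- Sections 4.0 and 5.0: reconcile the Visit 2 to Visit 3 interval with the diary week and the dosing period, for both combined and separate visits.

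No procedure is added, and drug can already be mailed. The cost is about a week between a combined visit and assignment, with a later contact to confirm that the diary is complete.

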### **4.0 Study Intervention(s)/Investigational Agent(s)**

Description:

Intervention: brivaracetam or placebo administration. [name] (Co-I/study physician) currently holds an Investigational New Drug (IND) application for brivaracetam to treat severe neuropathic pain in individuals with SCI (IND # 150388). With regulatory support provided by UMN CTSI, we will submit this protocol to the FDA for review under the existing IND upon notification of funding. RxArtisans Pharmacy (Wayzata, MN) will FedEx the drug to the participant directly (study staff will send an email notification to the participant that the drug has been sent by overnight

mail) or to the designated contact at the enrolling site for distribution. To minimize wasting of drug, RxArtisans will dispense and ship prescriptions concurrent with the ramp-up schedule (weekly, biweekly, or as requested by study doctor). Participants will be asked to verify by phone or email receipt of study drug and initiation of the treatment course.

Drug dosage will be individually titrated for each participant with a goal of 100mg BID according to the following dose escalation protocol that we use clinically: 50mg BID for 1 week followed by 100mg BID for 28 days as tolerated. Participants will be allowed to reduce the dose of brivaracetam if they experience unacceptable side effects defined as increased somnolence according to routine clinical practice with other drugs in this class used for pain. Participants will be given an additional week to ramp up to 100mg BID, as needed. The 28-day treatment period might also be extended in the case of illness or other unanticipated event that impacts the ability to take the medication consistently. This will be determined on a case-by-case basis by the study team. The treatment course will be recorded and considered in analysis. A dose of 50mg BID or higher must be maintained to complete the trial. The study drug will be paid for by the study.

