Drug discontinuation at study completion will be done according to the following protocol we use clinically that will be initiated for 2 weeks following end of study testing (Visit 3): reduction to 50mg BID for 1 week followed by 50mg daily for 1 week. For those at the highest study tolerated dose of 50mg BID, the dose will be reduced to 50mg daily for 1 week and then stopped. At the end of the two-week ramp down, participants will mail any remaining pills and the empty pill bottle along with the medication diary using self-addressed and prepaid packaging. University of Minnesota Investigational Drug Services (IDS) will register the study, while Rx Artisans will be dispensing the drug.

If a participant is admitted to the hospital for any reason during the course of the study, the participant or physician will notify the study coordinator or study PI using the phone number contained on the consent form or printed on the medication bottle. The PI/study coordinator will immediately notify the blinded study physician ([name]) who will contact the unblinded medical monitor ([name]). The two will decide whether unblinding is warranted. If warranted, the medical monitor will access the unblinding key that is stored in a password-protected file that only he and the pharmacy can access. The medical monitor will follow up with the treating physician and provide

the drug information (i.e., placebo or study drug) within 30 minutes of notification. The process for emergent unblinding will be available 24 hours a day, 7 days a week.

At the beginning of the study, all participants are directed that if in this situation, they are to bring study medication to the hospital and inform the physician overseeing the hospital stay that they are taking a research-related study drug. Further, the medical professional should assume that they are on the study drug. He/she may reach out for more information about the study drug.

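### Visit 3 is timed from Visit 2 but the regimen runs from first dose, so target-dose days can be lost; two places also overstate treatment time before Visit 3

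*Combined protocol and SAP*

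**What the plan says.** - **Visit 3 (Section 5.0).** "End of intervention assessments will be repeated 5 weeks after Visit 2".
- **Regimen (Section 4.0).** "50mg BID for 1 week followed by 100mg BID for 28 days as tolerated". Study Design in Section 5.0 likewise gives four weeks at full dose.
- **Flexibility (Section 4.0).** "Participants will be given an additional week to ramp up to 100mg BID, as needed". The next sentence adds: "The 28-day treatment period might also be extended in the case of illness or other unanticipated event", to be decided case by case. Neither sentence mentions Visit 3.
- **Taper (Sections 4.0 and 5.0).** The two-week dose reduction follows Visit 3, and staff give the instructions at the end of that visit.
- **Supply and start.** Table 1 dispenses drug at Visit 2. The text of Section 5.0 has a seven-week supply mailed on randomization, which takes place at Visit 1. Section 4.0 describes overnight shipment and says "RxArtisans will dispense and ship prescriptions concurrent with the ramp-up schedule". It also states: "Participants will be asked to verify by phone or email receipt of study drug and initiation of the treatment course".
- **Stated durations.** Aims 1 and 2 refer to a 7-week course. The paragraph in Section 5.0 on use of the Center for Magnetic Resonance Research puts Visit 3 after the seven weeks are complete. Table 1 has a seven-week intervention column before the Visit 3 column. Aim 3 puts the second miR-485 sample after three months of treatment. Study Duration gives about 11 weeks per participant from enrollment, and Visit 4 falls one month after the last drug.
- **Analysis (Section 4.0).** "The treatment course will be recorded and considered in analysis". No method is given.

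**The concern.** There are two clocks. The regimen is counted from first dose and the visit that ends it is counted from Visit 2. Both run for 35 days, so there is no slack, and the protocol states no visit window. Anything that delays first dose or lengthens the ramp-up comes out of the 28 days at target dose unless someone moves Visit 3. The protocol does not say which rule prevails, so two coordinators could each follow a written sentence and deliver different exposures.

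At stake is the exposure behind the end-of-intervention pain rating, MRI and blood sample. The documents never name the time point of the primary endpoint; Visit 3 is the natural inference, because it carries the end-of-intervention assessments.

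The duration statements raise a separate reporting risk. An outcome measured after about 5 weeks of treatment could be described as an outcome after 7 weeks or three months, and this pilot is meant to inform larger trials.

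**Working it through.** **Inputs.** Visit 2 to Visit 3: 35 days (Section 5.0). Ramp-up: 7 days, or 14 with the extra week (Section 4.0). Target-dose period: 28 days (Section 4.0). Taper: 2 weeks (Section 4.0). Visit 4: one month after last drug, taken as 30 days or 4.3 weeks (Section 5.0). The lag from Visit 2 to first dose is not stated. I take 0 or 1 day as closest to overnight shipping and show 3 days as an assumed upper case.

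**1. The plan's own totals.**
- Time on drug: 1 + 4 + 2 = 7 weeks, matching the seven-week supply.
- Participation: 5 + 2 + 4.3 = 11.3 weeks, matching the stated 11 or so.

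The second sum starts at Visit 2, whereas Study Duration counts from enrollment. It therefore fits combined Visits 1 and 2, and separate visits add the gap between them. Both sums assume no lag and no extra ramp-up week.

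**2. Target-dose days if Visit 3 stays at Visit 2 + 35 days.**

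Days at 100 mg BID = 35 − lag − ramp-up days. Day on which Visit 3 would have to fall, counted from Visit 2, to keep all 28 = lag + ramp-up days + 28.

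| Lag (days) | Ramp-up (days) | Days at 100 mg BID | Change from 28 | Visit 3 day needed |
|---|---|---|---|---|
| 0 | 7 | 28 | 0% | 35 |
| 1 | 7 | 27 | −3.6% | 36 |
| 3 (assumed) | 7 | 25 | −10.7% | 38 |
| 0 | 14 | 21 | −25.0% | 42 |
| 1 | 14 | 20 | −28.6% | 43 |
| 3 (assumed) | 14 | 18 | −35.7% | 45 |

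The 21-day row with zero lag needs no assumption about delivery. It follows from the permitted extra week and the written visit rule.

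**3. Recall week of the pain rating.** The primary item asks about average pain over the last week. With D target-dose days, it covers days D − 6 to D: days 22–28 when D = 28, 15–21 when D = 21, and 12–18 when D = 18. In every row it lies wholly at 100 mg BID for those who reach that dose.

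**4. Which duration before Visit 3 fits.**

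| Treatment before Visit 3 | Weeks on drug | Weeks of participation |
|---|---|---|
| 5 weeks | 5 + 2 = 7 | 5 + 2 + 4.3 = 11.3 |
| 7 weeks | 7 + 2 = 9 | 7 + 2 + 4.3 = 13.3 |
| Three months (13 weeks) | 13 + 2 = 15 | 13 + 2 + 4.3 = 19.3 |

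Only the first row agrees with both the seven-week supply and about 11 weeks of participation.

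**The case against.** The strongest reply is that Section 4.0 governs. The regimen fixes 28 days at target dose, Visit 3 is defined by its function as the end-of-intervention assessment, and the five weeks are simply the nominal 7 + 28 days. The word *also* in the extension sentence suggests that the extra ramp-up week is meant to lengthen the course too, and a rigid Visit 3 would defeat the extension. This is a fair reading, and staff may well act on it. What remains is that no sentence moves Visit 3, and that the extension is tied to illness or unanticipated events, not to a routine start lag.

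Second, the lag may be trivial or absent. If drug is mailed on randomization at a separate, earlier Visit 1, it could be in hand by Visit 2. This stands, and it is why the extra ramp-up week carries the main figure.

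Third, the treatment course is to be considered in the analysis. That describes the variation but does not restore dosing days.

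Some stronger readings are tempting but not supported:
- **A routine one-week lag from the pre-drug diary.** This would give 35 − 7 − 7 = 21 target-dose days, or 35 − 7 − 14 = 14 with the extra week. It requires combined visits, a diary begun only after consent at that visit, and an unmoved Visit 3, all together. The documents do not say when the diary is handed out relative to these visits.
- **A between-arm bias, or a rating taken during the taper.** The visit rule is the same in both arms and study staff are masked. Visit 3 precedes the taper.
- **Table 1 and Aims 1–2 as errors.** Seven weeks is correct as total time on drug including the taper. Table 1's layout is ambiguous, not plainly wrong.

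**Conclusion.** The concern holds in this limited form. The visit rule and the regimen agree only with first dose on the day of Visit 2 and no extra ramp-up week. Followed literally, the extra week leaves 21 of 28 target-dose days (−25%), and a start lag removes days one for one, about one day (−3.6%) with overnight shipping and possibly none.

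This rests on Visit 3 not being moved, which the documents neither require nor rule out. They give no rate of slow titration, no lag data and no onset curve for pain relief, so neither the number of participants affected nor the effect on the outcome can be calculated. The consequence is shorter and more variable exposure in both arms.

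The imaging-centre paragraph in Section 5.0 and Aim 3 are wrong without any such condition: Visit 3 follows about 5 weeks of dosing, 4 of them at target dose. Severity is minor to should-fix.

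**What to change.** - **Visit rule.** Set Visit 3 at completion of the 28-day target-dose period, nominally day 35 from the verified first dose and before the taper. Move it day for day with any ramp-up or treatment extension under Section 4.0, so day 42 with one extra ramp-up week. See participants who stay at 50 mg BID on the same nominal day. If Visit 3 is the primary time point, say so.
- **Durations.** Change the imaging-centre paragraph in Section 5.0 and Aim 3 to about 5 weeks. Clarify in Table 1 that the seven weeks are 5 before Visit 3 and 2 of taper after it. State in Aims 1–2 and in the conclusions that end-of-intervention outcomes reflect about 5 weeks of treatment, 4 at target dose.

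The cost is wording and somewhat more flexible scheduling, with no new visit or measure. The anchor date should be available, because participants already confirm that they have started. Someone using the extra week needs up to 8 weeks of drug (2 + 4 + 2) and one more weekly call. The seven-week supply and the stated participation time should be reworded to allow for this; shipment already follows the ramp-up. The interval from first dose to Visit 3 would then vary with titration and should be tabulated by arm.
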